### 11.1 Analysis Plans for Primary Objective

**PSA Slope:** Eligible patients must have a rising PSA with a minimum of 3 time points but up to 17 time points (2 rises at least 21 days apart) within the 12 months prior to study initiation (this could include the PSA measurement taken at the screening visit, but not at the baseline day 0 study visit). The pre-treatment slopes will be calculated based on these data prior to baseline (day 0). A minimum of three time points but up to five time points will be used for calculating on-study slopes: baseline, 12, 24, 36, and 48 week assessments. All data points will be used unless an assessment is unavailable, in which case the remaining time points will be used. There must be a minimum of three data points, and there will be no imputation of missing PSA values.

The primary objective will be based on the intent-to-treat (ITT) population and assessed with an ANCOVA model, with post-treatment PSA slope as the independent variable and study arm and baseline PSA slope as covariates. A two-sided t test at the 0.05 significance level will be used to determine if, adjusting for baseline, the post-treatment PSA slope has been reduced with MPX supplementation (Arm A). Scatterplots of post treatment PSA slope by baseline slope will be used to visualize the fitted ANCOVA model. Boxplots of the observed changes will also be used to visualize the results.

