### **Stratification**

Stratification will be by pretreatment PSADT ( $\leq 9$  or  $>9$  months) and Grade Groups (Grade Groups 1 and 2, equivalent to Gleason  $\leq 3 +4$ , and Grade Groups 3, 4 and 5, equivalent to Gleason  $\geq 4 +3$ ).

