We expect the average DTs of patients enrolling on this study to be in the range of 6 to 15 months, which correspond to average log slopes of 0.1155 ng/mL/month and 0.0462 ng/mL/month respectively. The historical post-treatment average slope estimates from the previous Hopkins trial were 0.033 ng/mL/month (average PSA-DT of 21 months) on the MPX arm and 0.083 ng/mL/month (average PSA-DT of 8.4 months) on the control arm. We have powered this study using the difference in these historical estimates as the clinically relevant post-treatment difference to be detected in this study: 0.05 ng/mL/month (or a PSA-DT difference of 12.6 months). It should be noted that for the same log slope difference between treatment arms, if the average post-treatment PSA rates of change are greater (steeper slopes), the detectable difference in DTs would be smaller and if the rates of change are less (slopes are less steep) the detectable DT difference will be larger.

**Randomization:** Stratified randomization will be performed to maintain balance between the arms as much as possible. Stratification will be by pretreatment PSADT ( $\leq 9$  or  $>9$  months) and Grade Groups (Grade Groups 1 and 2, equivalent to Gleason  $\leq 3 +4$ , and Grade Groups 3, 4 and 5, equivalent to Gleason  $\geq 4 +3$ ). Block randomization, with varying block sizes, will be used to ensure reasonable balance between the arms. Randomization assignments will be generated by the study statistician prior to initiation of the study using an R (version 3.4), and made available to the study team through the study electronic database.

**End of Study:** The date the study ends for the purpose of the final analysis is the date at which all randomized subjects have either completed the study or prematurely discontinued treatment and withdrew. This date will be designated as the primary analysis date for data cutoff and for all statistical analyses of efficacy and safety. Following the collection and adjudication of all data for all randomized subjects (follow-up up to and including the primary analysis date for data cutoff, the study blind will be broken (Section 5.2, Blinding).

**Primary Objective:** Determine if men who display the AA genotype of MnSOD and supplement their diet with MPX have greater changes in PSA slope following treatment compared to men that do not supplement with MPX.

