**Sample size and accrual:** This two arm randomized study will determine if there are differences in the change in PSA slope (post supplementation minus pre supplementation) between patients supplementing with MPX (Arm A) and patients that are not (Arm B). The accrual rate for each site is expected to be 1 patient per month. With 16 to 17 sites, is expected that we could accrue 500 patients over 4 years, for which we will have baseline MnSOD genotype and baseline antioxidant status, of which approximately 80 would be of the required AA genotype and eligible for randomization to MPX or placebo. Overall the study would take 4 years of accrual and another year for follow-up. PSA slope will be defined by the linear regression line of the natural log of PSA (in ng/mL) against time (in months). The primary statistical analysis will be an analysis of covariance (ANCOVA) to compare the two arms at the final analysis, adjusting for baseline PSA slope. Implications of the sample size are given based on simulations which include a single interim analysis for futility midway through the trial. The predictive probability approach for the futility analysis is described in the interim analysis section below. Based on the previous study of MPX at Hopkins, we conservatively estimate that the difference in the post-treatment PSA slope (MPX minus placebo), adjusting for pre-treatment PSA, in this group of patients with the AA genotype will be -0.05 with the MPX arm having lower post-treatment slopes (MPX slope 0.033 ng/mL/month versus untreated 0.083 ng/mL/month). Patients with the AA genotype will be randomized to MPX (Arm A) and placebo (Arm B) in a 1:1 ratio. Using a two sided 5% type I error allowance, a sample size of 78 (39 per arm), and minimal correlation between the pre and post treatment PSA slopes, this study will have 83% power to detect a difference in post-study PSA slope of -0.05. Use of the ANCOVA design with covariate adjustment for pre-treatment PSA slope will tend to increase the power depending on the level of the correlation between paired PSA slope measurements (i.e., pre- and post-treatment). As an example, for a correlation ( $\rho$ ) of 0.30, the power would increase to 87%.

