**Interim analysis for primary objective:** We plan to monitor the primary efficacy objective for futility once, after treating half the planned number of patients (i.e., 39), using a predictive probability approach. The ANCOVA analysis for the primary objective is a linear regression using the post treatment PSA slope as the outcome and study arm and baseline PSA slope as covariates. The monitoring plan is based on calculations of the likelihood of a significant result if the trial were to continue to the end. At the time the trial is monitored, 100 simulations of the future results of the trial will be generated and analyzed. If the probability that the trial would end with a significant result falls below a cut off value, the study will be stopped for futility. In Bayesian linear regression, all the parameters are given a prior distribution. A common objective

prior for linear regression is the g-prior of Zellner. This prior uses the covariate information in the data to specify the prior variance for the regression coefficients. An inverse-gamma prior distribution is typically used for the residual variance,  $\sigma^2$ . We will use information obtained at the time of the interim analysis to describe the distributions of these parameters.

The interim analysis will occur after 50% of the patients ( $m=39$ ) have been treated and assessed for post-treatment PSA slope. At this time the ANCOVA model will be fit and the variance of the residuals,  $SSR_g$ , and the posterior distribution of the regression (ANCOVA) coefficients  $\beta$  will be calculated using the g prior with  $g = m$ . From this information, we predict the results of the trial by simulating the remaining future patients' data from the predictive distribution and performing an ANCOVA analysis on the combined interim data and simulated data. We will base the predicted probability of ultimately finding a significant difference on 100 simulations. The following steps will be used to generate the  $i^{th}$  simulated value.

1. Generate  $\sigma^{2(i)}$  from its inverse-gamma posterior.
2. Generate  $\beta^{(i)}$  from its (conditional) posterior distribution.
3. Generate  $\tilde{Y}_j, j=1, \dots, n-m$  from  $N(X_j \beta^{(i)}, \sigma^{2(i)})$
4. Perform the final ANCOVA analysis based on the interim data and the predicted data.
5. Repeat for the required number of simulations predicting the final outcome (100).

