6. Calculate the predicted probability of rejecting the null hypothesis at the end of the study.

If interim analysis simulations indicate that the probability of a successful trial would be less than 10%, we will consider stopping the trial for futility. The table below gives the operating characteristics of the monitoring plan based on 2000 simulations for different scenarios, each scenario corresponding to different treatment effects and different levels of correlation between the pre-treatment and post-treatment PSA slope. The seventh row shows results using the hypothesized treatment effect of a mean difference of -0.05 with a standard deviation of 0.075, and minimal correlation. We do expect some correlation between pre and post-treatment values, so power will tend to increase with increasing correlation. The significance level for the final analysis is 0.05. Scenarios 1-3 give operating characteristics under the null (no treatment effect).

**Table 1.** Operating characteristics of monitoring rule from 2000 simulated studies with one interim analysis based on 100 predicted study conclusions and final analysis based on an ANCOVA model. Simulations use a *g*-prior with  $g=39$  (i.e. the sample size at the time of the interim analysis). All simulations assume the standard deviation of post-treatment PSA slope is 0.075.

Scenario	Treatment Effect	Correlation (pre- and post-treatment measures)	Stop for Futility %	Would have stopped for Futility and would have Rejected %	Overall studies rejecting Ho %
1	0.0	0.1	34.0%	0.10%	4.3%
2	0.0	0.2	33.5%	0.35%	5.6%
3	0.0	0.3	34.5%	0.20%	4.4%
4	-0.025	0.1	21.9%	1.00%	31.8%
5	-0.025	0.2	20.4%	0.80%	30.6%
6	-0.025	0.3	17.5%	1.40%	35.0%
7	-0.050	0.1	4.5%	1.25%	82.7%
8	-0.050	0.2	4.4%	0.75%	81.9%

9	-0.050	0.3	3.0%	0.95%	87.3%
10	-0.075	0.1	0.4%	0.30%	98.8%
11	-0.075	0.2	0.4%	0.20%	99.1%
12	-0.075	0.3	0.2%	0.15%	99.7%

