## **11.2 Secondary Efficacy Assessment**

**PSA Doubling Time (PSADT):** The PSADT will be calculated as  $\ln(2)$  ( $=0.693$ ) /  $\beta$  ( $=$ slope of the linear regression fit to  $\ln$  PSA vs. time in months). If the patient's slope is less than or equal to zero, we will assign them a PSADT of 100 months, which is consistent with the literature.

A secondary statistical test of the difference between the two groups will be assessed by a nonparametric Wilcoxon Rank Sum test of the percentage change in PSADT (logarithm of the ratio of PSADT on-study divided by the pre-treatment PSADT). We will also analyze the log of the PSADT ratio by the analysis of variance (ANOVA) adjusted for the stratification factors. Confidence intervals (95%) for the change from baseline in PSADT will also be computed for the two dose groups. The paired t-test (or Wilcoxon signed-rank test) will be used to assess the within treatment group differences of PSADT on study compared to the baseline. Patients with negative slopes will be assigned PSADT of 100 months.

**PSA Reduction of  $\geq 50\%$  / Objective Response:** An objective response (OR) is defined as a decrease in PSA by 50% or more after the start of treatment. The objective response rate (ORR) is estimated as the fraction of men for whom an objective response is observed. The time to objective response, defined as the time from start of treatment to an observed objective response, as well as the average duration of response, defined as the time from objective response to disease progression, will also be summarized and compared between groups. To further summarize PSA responses, the percentage change in PSA from baseline at 24 and 48 weeks will be presented in the form of waterfall plots.

**PSA Progression:** The distribution of time to PSA progression will be estimated using Kaplan-Meier method for both treatment groups combined and separately. The stratified logrank test will be used to test the hypothesis that the time to PSA progression distributions for the 2 treatment groups are the same. The same stratification factors used for the randomization will be used to stratify the logrank test.

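### Grade Group is used to stratify randomisation but is missing from the primary and interim ANCOVA; adding it before the interim look costs almost nothing and gains 0 to about 2 power points

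*Combined protocol and SAP*

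**What the plan says.** Section 4.1 (Stratification) states: "Stratification will be by pretreatment PSADT", cut at 9 months, and by Grade Group, 1-2 against 3-5. Section 11 (Randomization) repeats both factors, gives the purpose as "Stratified randomization will be performed to maintain balance between the arms as much as possible", and specifies blocks of varying size.

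The primary model uses neither factor as such. Section 11 (Sample size and accrual) plans an ANCOVA "to compare the two arms at the final analysis, adjusting for baseline PSA slope". Section 11.1 describes it "with post-treatment PSA slope as the independent variable and study arm and baseline PSA slope as covariates". In that sentence, independent variable must mean the outcome, because the interim section describes the same regression as "using the post treatment PSA slope as the outcome and study arm and baseline PSA slope as covariates".

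Elsewhere the plan does use the strata. In Section 11.2 the secondary analysis of the log PSADT ratio is an "analysis of variance (ANOVA) adjusted for the stratification factors", and both logrank tests are stratified by the randomisation factors. Section 11.4 mentions adjusting the primary endpoint only as possible sensitivity analyses, for antioxidant intake or supplement use. No section adds Grade Group to the primary model.

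**The concern.** Stratifying on a prognostic factor removes most of its chance imbalance between arms, so the treatment estimate becomes more precise. A model that omits the factor leaves its variance in the residual, so the reported standard error is larger than the estimate's true variability. The test is then conservative and some power goes unused.

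Of the two factors, only Grade Group is really omitted. Section 11 defines PSADT as ln 2 divided by the log slope, so the PSADT stratum is a cut of the baseline slope already in the model. What is at stake is precision in a trial that expects to genotype about 500 men over 4 years to find about 80 to randomise. Validity is not in question.

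**Working it through.** **Inputs from the documents.** Section 11 (Sample size and accrual): 78 patients, 39 per arm, 1:1, two-sided 5%, difference -0.05, stated power 83% with minimal correlation and 87% at pre/post correlation 0.30. Section 11, Table 1: "All simulations assume the standard deviation of post-treatment PSA slope is 0.075". Interim rule: one look at 39 patients, g-prior with g = 39, 100 predictive draws, stopping considered if predicted success is below 10%.

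**Step 1: reproduce the stated power.** SE = 0.075 × √(1 - ρ²) × √(2/39).

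- ρ = 0.1: SE = 0.0169, and 0.05/0.0169 = 2.96. Power is 84.1% (normal) or 83.2% (t, 75 df), against 83% stated.
- ρ = 0.3: SE = 0.0162. Power is 87.0% (normal) or 86.1% (t), against 87% stated.

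**Step 2: size the unknown.** The documents give no link between Grade Group and slope. Let r be the partial correlation of Grade Group with post-treatment slope given baseline slope, and assume a 50/50 split. The implied slope difference between Grade Group strata is r × 0.075 × √(1 - 0.1²) / 0.5, which is 0, 0.015, 0.030 and 0.045 per month for r = 0, 0.1, 0.2 and 0.3. These are 0, 30, 60 and 90% of the hypothesised treatment effect of 0.05.

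**Step 3: simulate both models on the same trials.** Further assumptions: permuted blocks of 4 or 6 within the four strata, PSADT cut at the median baseline slope, Grade Group independent of baseline slope, and a variance prior worth one observation. There were 20,000 trials per cell with the look and 40,000 without. The Monte Carlo SE of the power change is 0.04 to 0.13 point.

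Check against Table 1 at r = 0, correlation 0.1: the planned model stops for futility in 5.2% of trials (Table 1: 4.5%) and rejects in 81.2% (82.7%). Under the null it stops in 36.7% (34.0%) and rejects in 4.7% (4.3%).

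| Assumed r | Power with look, correlation 0.1: planned → with Grade Group | Change with look, correlation 0.1 | Change with look, correlation 0.3 | Change without look, correlation 0.1 / 0.3 | Type I error of planned test, no look, correlation 0.1 / 0.3 |
|---|---|---|---|---|---|
| 0 | 81.2 → 81.0% | -0.15 | -0.09 | -0.03 / -0.04 | 5.0 / 4.9% |
| 0.1 | 81.7 → 81.9% | +0.26 | +0.26 | +0.24 / +0.20 | 4.9 / 5.0% |
| 0.2 | 82.1 → 83.0% | +0.98 | +0.89 | +0.97 / +0.88 | 4.8 / 4.7% |
| 0.3 | 82.9 → 85.3% | +2.39 | +2.02 | +2.36 / +2.02 | 4.0 / 4.1% |

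The planned model's own power rises down the table, from 81.2% to 82.9%. Stratified randomisation has already delivered part of the benefit, and the Grade Group term recovers the rest.

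**Step 4: standard error.** At r = 0.3 and correlation 0.1, the mean SE falls from 0.01690 to 0.01612. The ratio is 1.05, so the planned interval is about 5% too wide. With the look, type I error at r = 0.3 is 3.6% for the planned model and 4.6% with Grade Group.

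**Step 5: sensitivity.** With a 30/70 Grade Group split (no look, correlation 0.1), the change is 0.0, +0.9 and +2.2 points at r = 0, 0.2 and 0.3. A second simulation with blocks of 2 and 4, 80,000 trials per scenario and the look included gives about -0.2, +0.5, +1.2, +2.4 and +3.6 points when Grade Group explains 0, 2, 5, 10 and 15% of the residual variance. For comparison, r = 0.3 corresponds to 9%.

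**The case against.** The strongest reply is that nothing here is wrong. Adjusting for fewer factors than were stratified on is allowed, the test is valid and the stated power holds. That is correct.

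The top of the range can also be attacked. A gain of 2 points needs r = 0.3, a slope difference of 0.045 per month between Grade Group strata. Section 11 expects average slopes from 0.0462 to 0.1155, a width of 0.0693, so this is about 65% of that whole range. At pre/post correlation 0.1, baseline slope explains 1% of outcome variance, while Grade Group would explain 9% of the remainder. The documents neither support nor exclude this. At r = 0.2 the gain is just under 1 point, and at 0.1 or below it is 0.3 point or less. If Grade Group does not predict slope there is a small loss, 0.03 to about 0.2 point. All of this stands, and it is why the result is given as a range that includes zero.

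A strata-adjusted comparison of PSA kinetics is already planned in Section 11.2. It is secondary, however, and does not sharpen the primary test. Finally, the documents do not say whether the interim look has been taken, and if it has, the primary gain is no longer available. That also stands and shapes the fix.

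Several simulation inputs are assumed, and the simulated null futility rate is somewhat above Table 1. Fitting both models to the same trials protects the differences more than the absolute power levels.

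**Conclusion.** The point holds as a minor efficiency gain to consider. Grade Group is a randomisation factor that neither the primary nor the interim model uses, directly or through another covariate. Adding it changes power by about -0.2 to +2.4 points for an assumed partial correlation of 0 to 0.3, and by less than 1 point up to 0.2. The planned test is clearly conservative only near 0.3 (type I error about 4%). These figures rest on the plan's SD of 0.075 and difference of -0.05, and on the assumed Grade Group split, block sizes, independence from baseline slope and variance prior. The prognostic strength of Grade Group is the decisive unknown, so confidence in the size is medium. The omission itself is plain in the text.

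**What to change.** Before the interim futility analysis is run, specify the primary model as post-treatment slope on arm, continuous baseline slope and the two-level Grade Group stratum. The PSADT stratum need not be added. Use the same model in the predictive simulation, drawing baseline slope and Grade Group as pairs from the 39 interim patients for the simulated future patients. While editing Section 11.1, name post-treatment slope as the outcome.

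Waiting until the blind is broken at the end of the study would be too late, because the interim analysis already fits a model containing study arm: "At this time the ANCOVA model will be fit". If that analysis has been done, keep the planned model as primary and add the Grade Group model as a sensitivity analysis.

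The cost is an amendment to three model statements (Sample size and accrual, Interim analysis, Section 11.1), a small change to the predictive algorithm and a rerun of Table 1. The rerun needs more than 2000 trials per scenario: √(0.827 × 0.173 / 2000) is 0.85 point, too coarse to show a 1-point change. Grade Group is already recorded for randomisation. The statistical cost is one residual degree of freedom (75 to 74).

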## **11.2 Secondary Efficacy Assessment**

**PSA Doubling Time (PSADT):** The PSADT will be calculated as  $\ln(2)$  ( $=0.693$ ) /  $\beta$  ( $=$ slope of the linear regression fit to  $\ln$  PSA vs. time in months). If the patient's slope is less than or equal to zero, we will assign them a PSADT of 100 months, which is consistent with the literature.

A secondary statistical test of the difference between the two groups will be assessed by a nonparametric Wilcoxon Rank Sum test of the percentage change in PSADT (logarithm of the ratio of PSADT on-study divided by the pre-treatment PSADT). We will also analyze the log of the PSADT ratio by the analysis of variance (ANOVA) adjusted for the stratification factors. Confidence intervals (95%) for the change from baseline in PSADT will also be computed for the two dose groups. The paired t-test (or Wilcoxon signed-rank test) will be used to assess the within treatment group differences of PSADT on study compared to the baseline. Patients with negative slopes will be assigned PSADT of 100 months.

**PSA Reduction of  $\geq 50\%$  / Objective Response:** An objective response (OR) is defined as a decrease in PSA by 50% or more after the start of treatment. The objective response rate (ORR) is estimated as the fraction of men for whom an objective response is observed. The time to objective response, defined as the time from start of treatment to an observed objective response, as well as the average duration of response, defined as the time from objective response to disease progression, will also be summarized and compared between groups. To further summarize PSA responses, the percentage change in PSA from baseline at 24 and 48 weeks will be presented in the form of waterfall plots.

**PSA Progression:** The distribution of time to PSA progression will be estimated using Kaplan-Meier method for both treatment groups combined and separately. The stratified logrank test will be used to test the hypothesis that the time to PSA progression distributions for the 2 treatment groups are the same. The same stratification factors used for the randomization will be used to stratify the logrank test.

**Disease Progression (Metastatic disease):** The distribution of time to disease progression will be estimated using Kaplan-Meier method for the treatment groups combined and separately. The stratified logrank test will be used to test the hypothesis that the time to disease progression distributions for the 2 treatment groups are the same. The same stratification factors used for the randomization will be used to stratify the logrank test.

**Toxicity Assessments:** Safety analyses will be performed on all subjects that received at least one dose of MPX. The proportion of toxicities by type and grade according to the Common Terminology Criteria for Adverse Events (CTCAE) version 5.0 will be reported with exact binomial 95% confidence intervals for each arm of the study.

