## 11. EVALUATION AND STATISTICAL METHODS

**Study design:** This is a multicenter, double-blind, randomized study to evaluate the benefit of MPX supplementation in the subset of men who display the AA genotype of MnSOD. Based on a previous randomized phase II trial of MPX at Hopkins, PSA doubling time (PSA-DT) was prolonged in this subgroup of men.

The primary objective of this trial will be to determine how the rate of change in PSA is affected by MPX supplementation and compare this treatment effect to a control arm given a placebo.

The rate of change in PSA, before and during treatment, for each patient will be quantified using the log slope which is calculated from a regression model of the log of PSA values on time. This quantity is the estimate directly used in the standardized method for the calculation of PSA-DT (PSA-DT is calculated as the natural log of 2 divided by the log slope).

Different PSA kinetic measurements have previously performed differently in different settings. In a randomized clinical trial, it is convenient if the distribution of the outcome to be compared between groups is suitable for analysis with a parametric test. The distribution of log slope, or the change in log slope, can reasonably be assumed to be approximately normal. By comparison, PSA-DTs are problematic when PSA values are not increasing exponentially, as in the setting where treatment may result in a PSA-DT less than zero. In this case the DT for the patient is assigned an arbitrary large value and any calculated changes in DT will necessarily involve this imputed value. As a result, assumptions of normality for the distributions of DTs, and changes in DTs, are not be reasonable, and would preclude parametric analyses. The log slope as a continuous quantity is therefore the chosen kinetic for this randomized clinical trial.

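### The 100-month PSADT rule covers flat or falling PSA but leaves barely rising PSA uncapped, so a rising PSA can outscore a falling one and one or two men can dominate month-scale means and intervals

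*Combined protocol and SAP*

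**What the plan says.** Section 11.2 (PSA Doubling Time) sets the rule: if the "slope is less than or equal to zero, we will assign them a PSADT of 100 months". The same section restates the trigger more narrowly: "Patients with negative slopes will be assigned PSADT of 100 months". No section gives an upper limit for PSADT when the slope is positive.

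These values feed four analyses in Section 11.2:
- a Wilcoxon rank sum test between arms on the log of the ratio of on-study to pre-treatment PSADT;
- an ANOVA of that log ratio, adjusted for the stratification factors;
- within-arm intervals: "Confidence intervals (95%) for the change from baseline in PSADT will also be computed for the two dose groups", with neither the method nor the scale given;
- a within-arm test: "The paired t-test (or Wilcoxon signed-rank test) will be used", with no rule for choosing between the two.

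Section 11 (Study design) explains why log slope was preferred to doubling time for the primary analysis. On a PSADT below zero it says: "In this case the DT for the patient is assigned an arbitrary large value". It concludes that "assumptions of normality for the distributions of DTs, and changes in DTs, are not be reasonable, and would preclude parametric analyses".

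**The concern.** A flat or falling PSA is the best outcome on this scale, so the value assigned to it should sit at the top. Under the written rule it does not. As a positive slope approaches zero, ln 2/slope grows without bound. As soon as the slope reaches zero, the score drops back to 100. Men just on the rising side of zero therefore outrank men whose PSA fell.

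The reversal enters every PSADT analysis. On the month scale it does more, because one near-flat man can contribute several hundred months to a 39-man mean. Estimating PSADT in the two groups is the first-listed secondary objective (Section 1.2), so what is at stake is the estimate itself: the mean change, its interval, and the paired t-test if run in months. The t-test option also sits badly with Section 11's own statement about normality.

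**Working it through.** **Inputs.** From Section 11: mean post-treatment log slopes 0.033 (MPX) and 0.083 (placebo) per month; 39 men per arm; two-sided 5%; slopes taken as approximately normal. From the Table 1 caption: "All simulations assume the standard deviation of post-treatment PSA slope is 0.075".

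**The plan's own figures reproduce.** ln 2/0.033 = 21.0 months and ln 2/0.083 = 8.4 months, difference 12.6. For power, 0.05/(0.075 × √(2/39)) = 2.944, and Φ(2.944 − 1.960) = 83.7%. The ANCOVA version (noncentral t, 75 df, correlation 0.1, ignoring the futility look) gives 83.2%. The plan states 83%, and 82.7% in Table 1.

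**Where the reversal occurs.** PSADT exceeds 100 when 0 < slope < ln 2/100 = 0.00693 per month. Over 48 weeks (11.04 months) that is a rise of less than about 8%. With a 9-month baseline:

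| On-study slope | Rise over 48 weeks | PSADT (months) | Log ratio |
|---|---|---|---|
| zero or negative | none | 100 | ln(100/9) = 2.41 |
| 0.003 | 3.4% | 231 | 3.25 |
| 0.001 | 1.1% | 693 | 4.34 |

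**How often.**
- Slope ≤ 0: Φ(−0.033/0.075) = 0.330 on MPX and Φ(−0.083/0.075) = 0.134 on placebo. Men assigned 100: 39 × (0.330 + 0.134) = 18.1 of 78.
- Slope between 0 and 0.00693: 0.0341 and 0.0210. Men above 100: 39 × (0.0341 + 0.0210) = 2.15.
- At least one such man: 1 − 0.9659³⁹ × 0.9790³⁹ = 0.887.
- For slope SDs of 0.03 to 0.10, these become 5 to 22 men assigned 100, 1.8 to 2.4 men above 100, and an 84% to 92% chance of at least one.

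**Leverage of one man.** Scoring 693 instead of 100 moves a 39-man mean by (693 − 100)/39 = 15.2 months. As an illustration, take 39 PSADTs evenly spaced from 8 to 34 months with a baseline of 9. The mean change is 12.0 (95% CI 9.5 to 14.5). Replacing the top man's 34 by 693 gives 28.9 (−6.1 to 63.9); replacing it by 100 gives 13.7 (8.9 to 18.5).

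**Simulation.** Pre-treatment PSADT was taken as lognormal with median 9 months and log-SD 0.4. This is an assumption, placed within the 6 to 15 months that Section 11 expects. Strata were omitted. The pre/post correlation was 0.1 unless stated.

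*Within arm, months (20,000 trials; signed-rank 2,000):*
- Uncapped men shift the MPX mean by more than 12.6 months in 24% of trials (18% to 37% for SD 0.10 down to 0.03).
- MPX t-interval width: median 31.6 months uncapped against 27.5 capped; 90th percentile about 120 to 135 across runs against 29.
- MPX paired t-test: significant in 91% uncapped and 100% capped; signed-rank 99.5% in both.
- Placebo, where the median change is about zero: paired t-test significant in 73% uncapped and 87% capped; signed-rank 20%.

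*Between arms (4,000 trials), uncapped against capped:*
- Wilcoxon 75.2% against 75.9%; at correlation 0.3, 79.7% against 80.0%.
- t-test on the log ratio 74.2% against 76.7%; at correlation 0.3, 77.5% against 80.2%.
- Null rejection is 4.8% to 5.4% throughout.

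A second simulation with a different assumed baseline (pre-treatment slopes averaging about 0.09, SD about 0.03) gave Wilcoxon 73.0% against 72.7%. In it, the chance that the placebo mean change in months exceeds the MPX mean change, despite the true effect, fell from 9.4% uncapped to 0.8% capped.

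**The case against.** The strongest reply is that the large numbers all need a mean in raw months, which the plan never specifies. The only change measure that Section 11.2 defines is the log ratio. On that scale the MPX t-interval width (median and 90th percentile) is 0.83 and 0.93 uncapped against 0.80 and 0.87 capped, so no single man dominates. That is correct. But change from baseline in PSADT reads naturally as months, and Section 2.2.3 reports the earlier trials that way. The plan leaves the choice open.

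Second, with medians and the signed-rank test, which Section 11.2 already allows, the cap hardly matters. The distribution-free interval for the MPX median change is 82.0 months wide uncapped and 81.7 capped. This also stands. It is a reason to commit to those methods, and it does not repair the ordering.

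Third, the between-arm effect is negligible. For the Wilcoxon test the two simulations differ in direction, so that difference is noise. Section 11.4 also labels everything but the primary outcome as secondary or lower. Both points are accepted and limit the weight of the finding.

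Fourth, the two trigger wordings hardly conflict, since a fitted slope of exactly zero is very unlikely, and the ANOVA is on a log scale that Section 11's remark does not directly address. Both are fair. The firm contradiction with Section 11 is the paired t-test in months.

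**Conclusion.** The concern holds. The ordering error follows from the written rule and needs no distributional assumption: at equal baseline, a slope between 0 and 0.0069 per month scores better than a falling PSA. At the plan's design values it is likely to arise (89% chance, about 2 of 78 men), and it can swamp a month-scale mean or t-interval. Those frequencies rest on normal slopes with SD 0.075; the month-scale simulation results also rest on an assumed baseline distribution.

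The reach is limited. The primary ANCOVA on log slope is untouched, type I error of the between-arm tests is not inflated, and the power cost to those tests is 0 to 3 percentage points. The damage falls on within-arm estimates for the first-listed secondary objective. The sponsor should correct it before unblinding, but it does not threaten the trial's main conclusion.

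**What to change.** Replace both trigger sentences in Section 11.2 with one rule, applied to pre-treatment and on-study values alike: PSADT is 100 months for every slope at or below ln 2/100 = 0.0069 per month, and ln 2/slope otherwise.

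Also state that:
- the Wilcoxon rank sum test of the log ratio is the PSADT group comparison and the ANOVA is supportive;
- the signed-rank test is used within arms, because the cap alone does not rescue the paired t-test (the placebo figures above get worse with it);
- change in PSADT is reported as a median with a distribution-free interval, flagging any limit that falls at the cap.

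The cost is two or three sentences of SAP text and no new data. There are two drawbacks. Flat, falling and barely rising men become tied at 100. And under the plan's slopes the MPX interval for median change remains about 82 months wide, with its upper limit set by a capped man in about 71% of trials.
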